### **8.5. Day -1 Baseline and Final Eligibility Assessments Evaluated at Clinic Intake**

If the subject is eligible after performing all the initial screening assessments, s/he will be scheduled to start the study and will come to the clinic for a final eligibility check and complete the baseline assessments on Day -1. A sentinel cohort of 2 subjects (1 assigned to receive kindolor tosylate and 1 assigned to receive placebo) will be dosed and closely monitored for at least 24 hours after receiving drug for AEs, prior to clinic intake and dosing the remaining 6 subjects in each successive cohort. No more than 2 subjects will be dosed on a single day of these 6 subjects.

For final eligibility determination, the following will be assessed at clinic intake on Day -1:

- Medical/Surgical History update
- Physical Examination update
- Weight
- Vital Signs
- Birth control methods for men and women update
- Pregnancy test (women only) (must be obtained within 72 hours prior to dosing)
- Prior and Concomitant medications

For baseline, the following will be performed:

- Clinical laboratory tests including chemistry, amylase, lipase, hematology, coagulation, urinalysis, and urine drug/alcohol screen
- FOBT

Blood for DNA genomics will be collected if the subject is still eligible.

The screening period will not be extended. If the investigator determines that the subject could be a viable participant who could not for extenuating circumstances complete the screening period in 30-days, the subject can be re-screened by completing all of the screening assessments again. In this case, the subject will be assigned a new subject number.

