Eligible subjects will undergo intake procedures at the UCSD Clinical and Translational Research Institute Phase I unit on Study Day -1 (the day before starting dosing) and will complete final screening and baseline evaluations. On Study Day 1, subjects will receive the study drug after an overnight fast (about 8 hours) with no food allowed until 4 hours after dosing. Study drug tablets will be administered with 240 mL of water. Water will be allowed anytime except for one hour before and after dosing. Subjects will remain in the unit for at least an additional 48-hours for safety assessments and blood collections to determine plasma levels of kindolor. Pre-dose assessments will be conducted prior to administration of study drug on Study Day 1. Blood for PK analysis will be collected ~ 15 minutes prior to dosing, then at 0.25, 0.5, 1, 1.5, 2, 4, 8, 12, 24, and 48 hours after dosing. Safety will be assessed by collecting adverse events (AEs), vital signs, physical examination, ECG, FOBT, Stool Consistency Questionnaire, GI Signs and Symptoms Checklist, urine output (24 hours) and clinical laboratory tests (amylase, lipase, chemistry, hematology, coagulation tests, pregnancy tests, and urinalysis). AEs will be assessed daily after the start of dosing, with closer evaluations in the 4-hour period after the start of dosing. Sitting (3 minutes) vital signs will be taken during screening, at clinic check in, pre-dose, then at 15, 30, 60 minutes and 2, 4, 6, 12, 24, and 48 hours post dose. A 12-lead ECG will be obtained prior to dosing, then at 2, 6, 12, 24, and 48 hours post dose. When vital signs or ECG are scheduled at the same time as a PK blood draw, these assessments will be performed before drawing any blood. The FOBT will be performed at screening, clinic intake on Day -1, pre-discharge on Day 3, and at follow-up on Day 7. Subjects will return for a final follow-up visit 7 ± 2 days after discharge for a final safety assessment including ECG, vital signs, AEs, FOBT Stool Consistency Questionnaire, GI Symptoms Checklist, and clinical laboratory tests. Males will be contacted 90 days and females 28 days after study drug administration to verify continued contraceptive use and having not donated sperm for males and have not breast fed a baby or donated ova for females during this period. The study schedule of visits and assessments is shown in [Table 6](#).

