## **8.7. Measures Taken to Minimize/Avoid Bias**

### **8.7.1. Randomization**

Each of the first two subjects in each cohort will be randomized to receive kindolor tosylate or Placebo. The remaining 6 subjects in the cohort will be randomized in a 5:1 ratio to receive kindolor tosylate or Placebo. As much as possible, groups will be balanced with respect to gender during randomization.

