### **8.13.2. Dose Continuation, Dose Escalation and Study Stopping Criteria**

Continuation of dosing within a cohort, or dose escalation to sequential cohorts will stop when either:

- a) The highest dose is reached or,
- b) Clinical/laboratory/AE findings meet any of the following stopping criteria:
  - i. Two or more subjects on active medication have clinical laboratory values meeting the criteria of moderate (Grade 2) intensity
  - ii. Two or more subjects on active medication experience moderate AEs of the same type (within the same MedDRA SOC)
  - iii. One or more subjects on active medication experiences any clinical laboratory value meeting the criteria of severe (Grade 3 or 4) intensity or an AE is determined to be severe in intensity
  - iiii. Any subject has a positive FOBT
- c) The mean kindolor systemic exposure levels exceed  $AUC(T_{last})=87,550$  ng.h/mL or  $C_{max} > 13,490$  ng/mL in a single subject in a cohort.
- d) The DSMB recommends stopping escalation after review of all the data from each cohort.

The maximum tolerated dose (MTD) will be considered the highest dose where no active medication subjects meet the study stopping criteria.

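### The remaining six subjects of a cohort can begin dosing before the sentinels' Day 3 laboratory and FOBT results are read, although Section 8.13.2 makes those results grounds to stop dosing within the cohort

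*Protocol*

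**What the plan says.** Protocol Section 8.13.2 covers dosing inside a cohort as well as escalation: "Continuation of dosing within a cohort, or dose escalation to sequential cohorts will stop when either" the top dose is reached or a listed finding occurs. Two of the listed findings need only one person. One is "One or more subjects on active medication experiences any clinical laboratory value meeting the criteria of severe (Grade 3 or 4) intensity"; the other is "Any subject has a positive FOBT". Section 11.1.5 adds that bleeding confirmed by FOBT stops the study.

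Section 8.5 sets the release of the rest of the cohort. In each cohort one active and one placebo sentinel are "dosed and closely monitored for at least 24 hours after receiving drug for AEs, prior to clinic intake and dosing the remaining 6 subjects". After that, "No more than 2 subjects will be dosed on a single day of these 6 subjects".

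On timing, Section 5 states: "The FOBT will be performed at screening, clinic intake on Day -1, pre-discharge on Day 3, and at follow-up on Day 7". The Schedule of Visits and Assessments places chemistry, hematology, coagulation, amylase and lipase at screening, Day -1, Day 3 and follow-up, with none on Day 1 or Day 2. The first post-dose laboratory and FOBT samples are therefore both due on Day 3.

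Sections 1 and 5 word the release more loosely: 24 h of monitoring before dosing, with no mention of intake. SAP 3.2 repeats that wording in the past tense.

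**The concern.** A within-cohort stop can act only on results that are in hand. The active sentinel alone can meet the Grade 3-4 laboratory criterion, and either sentinel can meet the FOBT criterion. Yet the condition for releasing the other six is AE monitoring that can end about a day before the samples behind those criteria are due. The documents contain no requirement that the sentinels' Day 3 results be read first. The DSMB reviews data after a whole cohort is complete, and the continuous review in Section 10 is not a condition for dosing.

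The findings at issue are ones this drug might produce. Section 4.9 reports total bilirubin rises in rats and minipigs without matching histology or other chemistry changes, and stomach erosions and ulcers after repeated dosing. A silent laboratory change or occult bleed in the active sentinel could go unseen while more healthy volunteers receive the same dose.

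**Working it through.** The plan gives no figure to reproduce here, so the check is a calendar in hours after the sentinels' dose.

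**Inputs**
- Sentinels dosed at 0 h (Day 1). Day 3 samples at about 48 h (Section 5 and its schedule).
- Result read at 48 + T, where T is the turnaround. Sections 11.3 and 11.7 name the laboratories but give no time, so T is an assumption.
- Section 8.5: intake from 24 h, dosing the next day, at most two per day. Pairs are dosed at about 48, 72 and 96 h at the earliest.
- Sections 1 and 5: dosing from 24 h. With the same cap, pairs are dosed at 24, 48 and 72 h at the earliest.

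**Count.** Subjects dosed without the result = 2 × (number of pairs dosed no later than 48 + T).

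| Sentinel results read | Section 8.5 | Sections 1 and 5 |
|---|---|---|
| before dosing on Day 3 | 0 of 6 | 2 of 6 |
| later, with T under 24 h | 2 of 6 | 4 of 6 |
| T of 24 to under 48 h | 4 of 6 | 6 of 6 |

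Under Sections 1 and 5 the first pair, at 24 h, precedes even the drawing of the Day 3 samples. Section 8.5 is the stricter text, and the conclusion rests on it.

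**How many of these are on active drug.** Section 8.7.1 says: "The remaining 6 subjects in the cohort will be randomized in a 5:1 ratio to receive kindolor tosylate or Placebo". If the one placebo is equally likely in any of the six positions (an assumption), then:
- First pair: P(both active) = C(5,2)/C(6,2) = 10/15 = 2/3; mean 2 × 5/6 = 1.7.
- First four: P(all active) = C(5,4)/C(6,4) = 5/15 = 1/3; mean 4 × 5/6 = 3.3.

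**Which criteria the sentinels can trigger.** With one active sentinel, the criterion of two or more active subjects at Grade 2 cannot be met by the sentinels alone. The Grade 3-4 laboratory and FOBT criteria can.

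**Where it matters most.** The rat human-equivalent dose at the no-effect level is 8160 mg (Section 4.8). Dividing by each dose: 8160/100 = 81.6, 8160/300 = 27.2, 8160/900 = 9.1 and 8160/1800 = 4.5. The margin is smallest in the later cohorts.

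**The case against.** The strongest reply is that a 24 h hold for AEs is a deliberate design choice with several layers behind it. A nurse stays with each subject for 4 h, and vital signs and ECGs are frequent (Section 8.6). The GI checklist runs daily from Day 1, the stool questionnaire covers Days 1 and 2, and endoscopy is available on symptoms with its own study stop (Section 11.1.5). Extra laboratory samples are allowed at discretion (Section 11.3), ad hoc DSMB meetings are possible (Section 10), and at most two of the six are dosed per day. Doses are single and enteric coated, five minipig half-lives are 22 h, and the animal hepatic effects were reversible (Section 4.9).

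Much of this stands. Stomach toxicity with symptoms should be caught early: the first minipig sign was soft feces, which the stool questionnaire covers. What remains is a Grade 3-4 laboratory value or positive FOBT without symptoms. None of the listed safeguards guarantees a sight of those before release, and the half-life in humans is not yet known.

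Another reply is that a laboratory draw at 24 h, beside the existing PK sample, would be read before dosing at 48 h if T is under 24 h, with no days lost. That is a fair alternative for the laboratory values. It adds a sample and does nothing for the FOBT.

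Four stronger readings might be inferred, and the documents do not support them:
- *The protocol contradicts itself.* It does not. The 24 h is a minimum, and 8.13.2 still acts on results as they arrive.
- *All six are routinely dosed blind to the sentinel results.* Under 8.5, a turnaround below 24 h affects at most the first pair.
- *The yield of a hold can be read from the incidence rates in Section 12.4.* Those illustrate any AE in a dose group. No rate is given for silent laboratory or FOBT findings.
- *A sentinel hold closes the gap for everyone.* At the fastest 8.5 pace the first pair's own Day 3 samples fall at about 96 h, so later pairs can still be dosed before those are read.

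**Conclusion.** The point holds as a timing gap between the release rule in 8.5 and the within-cohort stops in 8.13.2. At the fastest pace under 8.5, 2 of 6 remaining subjects can be dosed before the sentinels' Day 3 results are read, unless those results are available before dosing that day. The figure is 4 of 6 if turnaround is 24 to under 48 h. These counts rest on an assumed turnaround and on the site using the minimum interval; it may go slower. The benefit of closing the gap is confined to findings that a sentinel actually shows, and its size cannot be estimated from the documents. The change is worth making because the samples are already scheduled and the people protected are healthy volunteers with no expected benefit.

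**What to change.** In Section 8.5, with matching wording in Sections 1 and 5, require that both sentinels' Day 3 laboratory results, and the FOBT if a stool has been passed, be reviewed before clinic intake of the first remaining pair. Holding intake rather than dosing avoids keeping admitted subjects waiting past Day -1. If a sentinel has passed no stool, release the pair on the laboratory results plus a negative GI checklist and stool questionnaire, and read the FOBT when it is obtained. State that results from later pairs continue to act under 8.13.2 as they arrive. SAP 3.2 needs no change.

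Cost against the fastest 8.5 pace (first pair at 48 h):
- Read the same day: intake at 48 h, dosing at 72 h, +1 day per cohort.
- Read by the next morning: intake at 72 h, dosing at 96 h, +2 days.
- T of 24 to under 48 h: intake at 96 h, dosing at 120 h, +3 days.

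Over four cohorts that is 4, 8 or 12 days. Taking the planned 6 months or so as 182 days, it is 2.2%, 4.4% or 6.6%. The delay uses up some of each remaining subject's 30-day screening window, and Section 8.5 is firm on that: "The screening period will not be extended". A SARS-CoV-2 or pregnancy test that falls outside its 72 h window may need repeating. No new type of procedure, staff or additional subjects are needed.

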### **8.6. Day 1 Dosing, and Pre- and Post-Dosing Assessments**

Urine output will be monitored over two 24-hour periods starting with the morning void on Day 1 and finishing through Day 3 prior to the morning void. The start time and end time of these two collection periods will be recorded and the amount collected during these 24-hour periods will also be recorded. After the subject is determined to be eligible and baseline assessments are completed, the subject will be randomized to treatment.

The dose of the assigned investigational product will be taken orally with approximately 240 mL of water after an approximate 8-hour fast and 4 hours before any food or beverage other than water to quench thirst under the supervision of study staff. Water can be given 1 hour after dosing.

Blood for PK will be collected ~ 15 minutes prior to dosing, then at 0.25, 0.5, 1, 1.5, 2, 4, 8, 12, 24, and 48 hours after dosing. Blood pressure and heart rate will be taken pre-dose, then 15, 30, 60 minutes and 2, 4, 6, 12, 24, and 48 hours post dose. If vital signs are more than 25% outside baseline levels, measurements will be repeated until they normalize.

A 12-lead resting ECG will be obtained prior to dosing, at 2, 6, 12, 24, and 48 hours post dose. A nurse will always stay with the subject for 4 hours after the dose and observe the subject for AEs and ask the subjects an open-ended question about how they are feeling and ask specifically about any epigastric discomfort.

#### **8.6.1. Confinement**

Subjects will be confined to the study site and supervised over a 4-day period starting on Study Day -1. Confinement will conclude after the scheduled study procedures are completed on Study Day 3. Strenuous activity during confinement will not be permitted.

#### **8.6.2. Meals, Dietary Requirements, and Other Restrictions**

Subjects will receive a standardized diet, providing approximately 30% of the daily calories from fat, for all meals during confinement. Subjects will start fasting on Study Day -1 after the evening meal and should be fasting for about 8 hours with no food allowed until 4 hours after dosing on Day 1. Starting with lunch on Study Day 1 until after the 24-hour blood collection on Study Day 3, the subjects will consume only the scheduled meals provided in the study and water to quench thirst. The subjects will abstain from all other food and beverage.

On the morning of dosing, non-caffeinated and nondairy liquids are permitted prior to dosing, but food is prohibited. No food or beverage, except for water to quench thirst, will be allowed on Study Day 1 from study drug dosing until after the collection of the 4-hour blood sample.

On Study Day 1 subjects will be served lunch following the 4-hour blood collection. The composition (protein, fat, carbohydrate, and total calories) of this meal will be determined by a dietician and a record will be kept with the source documents. The sequence of starting meals on the dosing days will be maintained such that the time intervals between dosing and meals are essentially the same for all subjects in each period. Subjects may not consume:

- Red meat, such as beef, lamb, or liver or raw fruits and vegetables,
- Alcohol within the 2-day period prior to any study drug administration,
- Grapefruit or grapefruit products during the study, or
- Caffeine during confinement.

Kindolor shows phototoxic potential, therefore, subjects will not be exposed to sunlight while in the Phase 1 unit and will be cautioned to limit exposure to direct sunlight after release and to apply a sun protectant lotion to exposed areas of the skin after release for at least another 24 hours.

## **8.7. Measures Taken to Minimize/Avoid Bias**

### **8.7.1. Randomization**

Each of the first two subjects in each cohort will be randomized to receive kindolor tosylate or Placebo. The remaining 6 subjects in the cohort will be randomized in a 5:1 ratio to receive kindolor tosylate or Placebo. As much as possible, groups will be balanced with respect to gender during randomization.

### **8.7.2. Blinding**

Only the research pharmacist will know the identity of the investigational product. The research pharmacist will keep the randomized assignment of subjects in a secure location. All other study staff will be blinded to treatment given. The site investigator or designated, approved study physician will make the decision to un-blind the identity of the investigational product if the study blind needs to be broken to make medical decisions regarding subject treatment. If it is determined that unblinding is necessary to assess AEs or SAEs for expedited reporting, the sponsor may decide to request unblinding of a subject.

## **8.8. Assessments on Days 2, 3 and at the Final Outpatient Visit**

Assessments (vital signs, laboratory tests, ECG, Stool Consistency Questionnaire, GI Signs and Symptoms Checklist, and AEs) on Study Days 2 and 3 will be evaluated in accordance with [Table 6](#). A final clinic visit will occur  $7 \pm 2$  days after the dosing day and will also be in accordance with [Table 6](#).

## **8.9. Final Telephone Contact**

Males will be contacted at Day 90 (+ 1 week) to verify continued use of contraceptives and to have not donated sperm during this period. Females will be contacted at Day 28 (+ 1 week) to verify continued use of contraceptives and to have not donated ova or started breastfeeding during this period.

## **8.10. Early Termination Visit**

If the subject requests to withdraw from the study early, early termination assessments will be scheduled if the subject agrees, and the assessments in [Table 6](#) will be performed.

## **8.11. Emergency Preparedness**

The Clinical and Translational Research Institute at UCSD is an 18,000 sq. ft. research clinic with over 20 clinic staff, research coordinators, and a Phase I unit. The Phase I unit is fully staffed by Advanced Cardiac Life Support certified nurses. The unit has all emergency equipment available in the event of a serious drug reaction. The facility has a 911 protocol with Emergency Medical Service available within 5 minutes for transport of the subject to the University of California Health System Emergency Room located across the street (door to door is less than 50 yards).

## **8.12. Duration of Subject Participation**

Each subject will participate in the study for up to approximately 58 days for females and 120 days for males, including up to 30 days for screening, 4 days and 3 nights residing in the Phase 1 unit, with one follow-up visit  $7 \pm 2$  days after discharge from the Phase 1 unit and a telephone call check at 28 days after dosing for females and 90 days after dosing for males for a verification contraceptive practices, and conformance with agreement not to donate ova, breastfeed, or donate sperm during this period.

## **8.13. Subject and Study Discontinuation and Stopping Criteria**

### **8.13.1. Discontinuation of Individual Subjects**

Each subject has the right to withdraw from the study at any time. In addition, the investigator may discontinue a subject from the study at any time if the investigator considers it necessary for any reason, including the occurrence of an AE or noncompliance with the protocol. Subjects who withdraw from the study will not be replaced unless it is mutually agreed upon, in writing, between the investigator and the sponsor.

Some specific considerations for replacement of subjects include:

1. If a subject is considered eligible for the study but does not receive any investigational product, another subject will be enrolled to ensure that each cohort has the target number of subjects.
2. If a subject is randomized to the active group but withdraws from the study before the Day 3 clinic release procedures are performed, then a replacement subject may be considered.
3. If a subject for some reason is missing safety measures such as clinical laboratory assessments, vital signs, or FOBT.
4. If a subject for some reason is missing blood samples for PK measurements such that PK cannot be determined.

If a subject withdraws or is discontinued from the study, the reason(s) for the discontinuation from the study will be recorded and a physical examination, body weight, vital signs measurement, ECG, laboratory analyses, Stool Consistency Questionnaire, GI Symptoms Checklist, and AEs will be performed as soon as possible after discontinuation from the study. Additional blood samples for drug measurement may be collected at the time of discontinuation from subjects who are discontinued due to AEs; the clock time, and date the sample was taken will be recorded.

If a subject is discontinued from the study with an ongoing AE or an unresolved laboratory result that is significantly outside of the reference range, the investigator will attempt to provide follow-up until a satisfactory clinical resolution of the laboratory result or AE is achieved.

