#### **11.1.3. Methods/Timing for Assessing, Recording, and Analyzing Safety Endpoints**

AEs will be assessed starting after the first administration of investigational product until the final follow-up visit. However, SAEs will be collected from the time of informed consent onward. General symptoms will be collected via an open-ended question: "How have you been feeling since your last visit or the last time we spoke?"

AEs will be documented in the source records and recorded on the eCRFs using accepted medical terms and/or the diagnoses that accurately characterize the event. When a diagnosis is

known, the AE term recorded on the eCRF will be the diagnosis rather than a constellation of symptoms. The investigator will assess all AEs for seriousness, relationship to investigational product, and severity. When an event has not resolved by study closure, it will be documented on the AE eCRF as “ongoing”.

All AEs, including clinically significant abnormal findings on laboratory evaluations, regardless of severity, will be followed by study physicians until satisfactory resolution (the event either resolved or stabilized and is not expected to resolve in the near term). AEs must be reported up to 1 week after investigational product administration. At the final clinic visit, AEs will be recorded and followed to resolution only if they are serious, or if the study physician assesses them to be clinically significant.

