### **11.2. Collection and Processing of Blood for PK Determinations**

Blood samples for determination of kindolor plasma concentrations will be collected by venipuncture within 15 minutes prior to dosing and at 0.25, 0.5, 1, 1.5, 2, 4, 8, 12, 24, and 48 hours after dosing. Blood will be collected as close to nominal times as possible and the date and time that each blood sample is collected will be recorded to the minute.

All plasma samples for each cohort will be analyzed for AUC(Tlast) and Cmax before enrolling the next cohort. If AUC(Tlast) exceeds 87,550 ng.h/mL or Cmax exceeds 13,490 ng/mL, then dose escalation will stop.

Further details on sample collection, processing, storage, and shipping are provided in the Manual of Procedures. Plasma concentrations will be determined using a validated liquid chromatography/mass spectrometry method.

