9.4 Study Drug Exposure

Study drug is given once per patient. Patient listing will be provided with date and time of administration, whether there was any problem with administration and specification of the problem.

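### Section 8.13.1 allows removal from the study after the only dose, for an AE or noncompliance, without requiring the remaining PK samples, FOBT or routine late laboratory tests

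*Protocol*

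**What the plan says.** **Removal.** Under Protocol 8.13.1, "the investigator may discontinue a subject from the study at any time if the investigator considers it necessary for any reason". The sentence covers removal "for any reason, including the occurrence of an AE or noncompliance with the protocol". It does not separate the time before dosing from the time after it. SAP 9.4 confirms that "Study drug is given once per patient".

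**After removal.** Section 8.13.1 requires one exit set: physical examination, weight, vital signs and ECG, and then "laboratory analyses, Stool Consistency Questionnaire, GI Symptoms Checklist, and AEs will be performed as soon as possible after discontinuation from the study". For drug levels it says: "Additional blood samples for drug measurement may be collected at the time of discontinuation from subjects who are discontinued due to AEs". For an ongoing AE or a result well outside the reference range, "the investigator will attempt to provide follow-up until a satisfactory clinical resolution of the laboratory result or AE is achieved". Nothing says that a removed subject continues the remaining PK samples or the Day 3 and Day 7 assessments.

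**FOBT.** After dosing it is scheduled on Day 3 and at the Day 7 follow-up only (Protocol section 5). It is not named in the 8.13.1 exit list. The FOBT row has no mark under Early Termination in the protocol's schedule of assessments or in SAP Table 1.

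**Decisions that use these data.** Section 8.13.2 makes a positive FOBT in any subject a stopping criterion and defines the MTD as the highest dose at which no active subject meets the stopping criteria. Section 11.2 says: "If AUC(Tlast) exceeds 87,550 ng.h/mL or Cmax exceeds 13,490 ng/mL, then dose escalation will stop".

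**The concern.** In a multiple-dose trial, taking a subject off the study may also take the subject off the drug. Here the whole exposure is given at one moment on Day 1, so removal after dosing can only reduce what is observed. Because an AE is a named reason, the loss can fall on the subjects whose later data matter most.

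Two decisions depend on those data.

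- **MTD.** A stopping criterion is met only by something observed, so a missing assessment can remove a trigger but cannot add one. For FOBT this matters because stomach toxicity is the main nonclinical finding (Protocol 4.9). A subject removed on Day 1 or 2 for a GI complaint could leave with no post-dose FOBT required.
- **Exposure limit.** AUC(Tlast) runs to the last quantifiable sample, so a curve cut short gives a lower value. Neither document says how such a value is read against the limit.

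The subject may also fall out of the PK population for want of sufficient concentrations, and 8.13.1 lets a replacement be considered.

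**Working it through.** **1. What each part of the text secures after removal**

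| Item | Required after removal? |
|---|---|
| Exit laboratory tests, ECG, vital signs, GI checklist, AEs | Yes, once (8.13.1) |
| Ongoing AE or unresolved laboratory result | Follow-up attempted to resolution (8.13.1); AEs followed to resolution (11.1.3) |
| Routine Day 3 and Day 7 laboratory tests, exit results unremarkable | No |
| Post-dose FOBT | Not scheduled |
| Remaining PK samples | No; sampling at exit is optional and mentioned only for AE removals |

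The post-dose PK times are 0.25, 0.5, 1, 1.5, 2, 4, 8, 12, 24 and 48 h. Removal after the 4 h sample leaves 4 of these 10 (8, 12, 24 and 48 h) and both post-dose FOBTs without a requirement.

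**2. Detection of an event**

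The plan's own figure (Protocol 12.4) is the chance of at least one event among 6 active subjects, 1 − (1 − p)^6. At p = 10, 15, 20 and 25% this gives 46.9, 62.3, 73.8 and 82.2%, which matches the stated 47, 62, 74 and 82%.

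For an event that only a later assessment would show, assume one of the six has left. Then 1 − (1 − p)^5 gives 41.0, 55.6, 67.2 and 76.3%. This treats leaving as unrelated to the event. The documents give no removal rate.

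**3. Shortening of AUC(Tlast)**

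Inputs: the minipig half-life of 3.21 to 4.36 h (Protocol 4.9), so ke = ln 2 / half-life = 0.216 to 0.159 per h. Assumptions not in the documents: a one-compartment oral model, absorption rate ka of 0.3 to 2 per h, and no lag.

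Fraction of AUC∞ reached by time t: F(t) = 1 − [ka·exp(−ke·t) − ke·exp(−ka·t)] / (ka − ke).

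- Lowest at 4 h (ke 0.159, ka 0.3): 1 − (0.3 × 0.529 − 0.159 × 0.301)/0.141 = 0.21.
- Highest at 4 h (ke 0.216, ka 2): 1 − (2 × 0.422 − 0.216 × 0.0003)/1.784 = 0.53.
- The same formula gives 0.51 to 0.80 at 8 h and 0.95 to 0.99 at 24 h.

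If six subjects have equal full exposure and one curve is cut at t, the cohort mean falls by (1 − F)/6:

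- 4 h: (1 − 0.53)/6 = 8% to (1 − 0.21)/6 = 13%.
- 8 h: (1 − 0.80)/6 = 3% to (1 − 0.51)/6 = 8%.
- 24 h: under 1%.

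If the limit were applied to each subject, a subject whose full AUC is 87,550 would show about 18,700 to 46,200 at 4 h (unrounded fractions 0.2132 and 0.5274).

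**4. The Cmax limit**

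In the same model tmax = ln(ka/ke)/(ka − ke), which is 1.2 to 4.5 h. A subject removed after the 4 h sample has therefore reached or nearly reached the peak. A lag from the enteric coat would weaken this and would lower F.

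**The case against.** The strongest reply is that the subjects who react are the ones the plan keeps following. Section 8.13.1 requires laboratory tests at exit and attempted follow-up of unresolved findings, and 11.1.3 follows AEs to resolution. This stands. A reader might infer that removal ends laboratory follow-up in those who reacted; the documents do not support that.

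A reader might also infer that new AEs after removal go uncollected. Section 11.1.3 says "AEs must be reported up to 1 week after investigational product administration", with no exemption for removed subjects. What is missing is a scheduled contact to elicit them.

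On exposure, 8.13.2(c) speaks of a mean for AUC and carries a separate Cmax limit, so one short curve moves the decision modestly. If the subject is left out of the PK population, the short AUC does not enter a summary of that population at all. A severe AE in one active subject, or moderate AEs in the same SOC in two, already stops escalation, and the DSMB sees each cohort's data. All of this stands. It rules out the stronger reading that removing a subject would by itself carry a cohort past the exposure limit.

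The rule is permissive, subjects are confined until Day 3, and removed subjects stay in the safety population. The 8.13.1 wording on drug samples is plural, so sampling is not capped at one. The exit GI checklist has a line for a positive FOBT (Appendix B), but a checklist line does not schedule a test.

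Finally, the investigator must be free to omit procedures for a subject's safety, for example in an emergency transfer. That is right, and the fix keeps it.

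**Conclusion.** The point holds as a gap in required data collection. Following 8.13.1 as written can lose PK samples, post-dose FOBT and routine late laboratory tests in a dosed subject, for reasons tied to the outcome, with no treatment left to stop. For the MTD the loss acts in one direction, towards a dose looking better tolerated.

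The FOBT part is the firmest. It rests only on comparing the exit list and the Early Termination column with the stopping criteria, and needs no model.

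The PK size is illustrative: about 8-13% off a six-subject mean AUC for one curve cut at 4 h, falling to under 1% at 24 h. It depends on animal half-lives, an assumed absorption rate, no lag, equal exposures and a chosen removal time. Human kinetics are unknown, and 11.2 does not say whether its AUC limit applies to the mean or to each subject. The detection figures (47 to 41% at a true rate of 10%, 82 to 76% at 25%) assume one removal unrelated to outcome, so they do not capture bias from AE-linked loss.

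**What to change.** - **Section 8.13.1.** State that after dosing, an AE or noncompliance does not by itself end scheduled data collection. The remaining scheduled PK, laboratory, ECG, FOBT and AE assessments continue through the final visit unless the subject withdraws consent or the investigator judges a procedure unsafe or impracticable.
- **FOBT.** Reconcile the 8.13.1 exit list and the Early Termination column (protocol schedule and SAP Table 1) with the FOBT stopping criterion in 8.13.2.
- **Section 11.2.** State that an AUC(Tlast) from a curve cut short by early exit is flagged to the DSMB and is not taken as evidence of being below the limit.

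The cost is a few sentences, some added effort to retain subjects after an AE, and an FOBT at early termination. The other assessments are already scheduled.
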